3.2. Sample Size Consideration

A sample of 40 subjects will be treated and analyzed to support regulatory approval. The sample size of 40 subjects is considered adequate to assess the primary safety endpoint, which is defined as the proportion of subjects experiencing a MAE within 30 days post-implantation.

Considering the reported MAE rate from the ENGAGE Post-Approval Study (PAS), which evaluated the long-term safety and effectiveness of the Endurant Stent graft system in 328 subjects¹, it is estimated that 2 of 40 (5%) subjects treated with Endurant Evo AAA stent graft system will experience a MAE. The precision of this assumed 5% point estimate can be assessed by calculating the difference from the 1-sided 95% upper confidence limit. This difference, or margin of error, is calculated to be < 10% for the Endurant Evo International Clinical Trial and is therefore considered adequate to assess the primary safety endpoint^{2,3}.

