4.1. Primary analysis set

All analysis will be performed on the intent-to-treat (ITT) analysis set, which includes all subjects who underwent the arterial access with an attempt to introduce the Endurant Evo AAA stent graft.

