8.1. General consideration

All endpoints will be analyzed descriptively. In general, qualitative parameters will be described by their distribution frequencies; quantitative parameters will be described by their mean, standard deviation, minimum, maximum, median, and number of subjects with assessable data.

The survival from all-cause mortality over one year time or longer will be described by the Kaplan-Meier survival curve and the associated Kaplan-Meier estimate will be calculated along with its standard error using the Greenwood method.

For events such as AEs, deaths and secondary procedures, that can occur or are observed at any time during the study, no time window will be applied. For such events, an event that occurs “within 1 month or 30 days” is an event that takes place between Days 0 to 30, inclusive.

Similarly, an event that occurs “within 12 months or 365 days” is an event occurring between Day 0 to Day 365, inclusive. Date of event onset will be used to determine when the event occurred. Day 0 is referring to the day of index procedure.

For image-based assessments, such as stent-graft endoleak, patency, and other observations, the following time windows will be applied for by-visit data summaries:

Table 1: Time Windows for Statistical Analyses

Study Visit	Target Day	Time Window
Implant	Day 0	Day 0
1 Month	Day 30	1 – 90 days
6 Months	Day 183	91 – 304 days
12 Months	Day 365	305 – 548 days
2 Year	Day 731	549 – 913 days
3 Year	Day 1096	914 – 1278 days
4 Year	Day 1461	1279 – 1644 days
5 Year	Day 1826	1645 – 2009 days

If different type of images are used but have different finding in the same time window, the imaging technique and sensitivity matrix (Appendix 12.1) will be applied. Finding from higher visibility image will be used for analysis. If there are two or more assessments from the same type of image in the same time window, then the assessment closest to the target day will be used in the analysis of event rate at a given time point.

Statistical analyses for this study will be performed using the Statistical Analysis System (SAS) for Windows (Version 9.1 or higher) or other widely-accepted statistical or graphical software.

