8.2. Baseline Characteristics and Poolability of Data

Summaries of subject disposition, demographics, baseline characteristics, and subject accountability will be provided.

Data from all geographies will be pooled for analysis. The poolability is assumed given that study data are collected and managed by a central database under one data management plan, including the use of Data Monitoring Committee (DMC), Clinical Event Committee (CEC), Independent Physician Reviewer (IPR) and core imaging laboratory.

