8.3. Handling of Missing Data

During statistical analysis, imputation of missing data will not be performed except for data related to the onset date of an adverse event or a death. In cases where the onset date of an event or a death is incomplete and unresolvable via data query, the 15th day of the known month or July 1st of the known year will be used.

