8.4. Analysis of the Primary Endpoints

For the primary endpoint, a one-sided 95% confidence interval based on binomial distribution will be constructed in addition to event count and frequency.

The analysis for the regulatory submission will take place when 40 subjects have been implanted with the study device for at least 30 days except that a subject expires early. Endpoints as defined in Section 5 will be analyzed for these 40 ITT subjects.

MAE Rate Calculation:

All MAEs will be adjudicated by the Clinical Event Committee (CEC) per protocol except for the procedural blood loss ≥ 1000 cc, which will be site reported at the index procedure. MAE rate will be calculated as follows (Table 2):

Table 2: MAE Rate Calculation:

MAE rate = $m/(m + k)$	Within 30 Days	Within 183 Days	Within 365 Days
$m = \text{No. of Subjects Who Had MAE(s)}$	No. of subjects who had at least one MAE with onset day from Day 0 to Day 30, inclusive.	No. of subjects who had at least one MAE with onset day from Day 31 to Day 183, inclusive.	No. of subjects who had at least one MAE with onset day from Day 184 to Day 365, inclusive.
$k = \text{No. of Subjects Who Had No MAE}$	No. of subjects who have been in study for at least 1 day and without an MAE.	No. of subjects who have been in study for at least 91 days and without an MAE.	No. of subjects who have been in study for at least 305 days and without an MAE.

If a subject is early terminated from the study, the last day that the subject has been seen will be the duration in study, which can be the day of last follow-up, last imaging taken, an AE reported, or withdrawal from the study. If a subject is still in the study, the duration in study will be the time from index procedure to the cut off day that the database is locked or data snapshot is taken.

Imaging based Event Rate Calculation:

Imaging assessment will be performed by site as well as the core lab. Assessments from the core lab will be analyzed separately from those by site. Imaging based event rate will be calculated using statistical analysis windows as follows (Table 3):

Table 3: Imaging based Event Rate Calculation:

Event rate = m/n	At 1 Month	At 6 Months	At 12 Months
$m = \text{No. of Subjects Who Had Event(s)}$	No. of subjects who had an event with scan day within the 1-month window.	No. of subjects who had an event with scan day within the 6-month window.	No. of subjects who had an event with scan day within the 12-month window.

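### SAP Table 2 counts a subject who exits on Days 1-29 with no recorded MAE as MAE-free for the 30-day primary safety rate, and the Protocol and SAP text ask for no bounding result

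*SAP*

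**What the plan says.** - **The rule.** In SAP 8.4 Table 2, the 30-day m is dated (MAE onset Day 0 to Day 30). k is "No. of subjects who have been in study for at least 1 day and without an MAE".
- **Time in study.** "If a subject is early terminated from the study, the last day that the subject has been seen will be the duration in study" (SAP 8.4). An exit on any of Days 1-29 therefore meets the 1-day requirement.
- **Analysis set.** "All analysis will be performed on the intent-to-treat (ITT) analysis set" (SAP 4.1), defined by arterial access and attempted introduction of the device. Protocol F.7 does not replace subjects who leave early.
- **Trigger.** The regulatory analysis is run "when 40 subjects have been implanted with the study device for at least 30 days except that a subject expires early" (SAP 8.4).
- **Missing data.** "imputation of missing data will not be performed except for data related to the onset date of an adverse event or a death" (SAP 8.3).
- **Event timing.** For events "that can occur or are observed at any time during the study, no time window will be applied" (SAP 8.1).
- **What would show early exits.** "Summaries of subject disposition, demographics, baseline characteristics, and subject accountability will be provided" (SAP 8.2). Table shells are in a separate document (SAP 11 and 12.2), which was not available here.
- **Reach of the rule.** SAP 8.5 uses Table 2 for mortality, secondary procedures, serious adverse events, conversions and ruptures as well.

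**The concern.** The endpoint covers Days 0 to 30, but membership of k requires one day. The thresholds for k (1, 91 and 305 days) equal the lower bounds of the 1-, 6- and 12-month imaging windows in SAP Table 1, although SAP 8.1 says events are not windowed. Nothing in the 30-day column asks whether the subject's status at Day 30 is known.

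Such exits are possible, though not planned. Subjects may withdraw at any time (Protocol F.7.2) or be lost to follow-up (F.7.4). Treatment failures leave the study after the 1-month time point (F.2.1.2), and the window for that visit opens on Day 15 (Table F-1). Some MAE definitions also need time to be met: paraplegia must persist for more than a month, and stroke deficits for more than 24 hours (Appendix L.2).

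At stake is the reading of the primary safety rate that was meant to support regulatory approval. A reader who sees x/40 cannot tell from that line whether all 40 outcomes were known.

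**Working it through.** **Inputs.** n = 40 and 2 expected MAEs, or 5% (SAP 3.2). One-sided 95% interval based on the binomial distribution (SAP 8.4). The number of exits on Days 1-29 without a recorded MAE, d, is in neither document; d = 0 to 2 is an assumption.

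**Formula.** Exact (Clopper-Pearson) one-sided 95% upper limit for x events in n: U = the 0.95 quantile of Beta(x + 1, n - x). Margin = U - x/n.

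**The plan's own figure.** SAP 3.2: "This difference, or margin of error, is calculated to be < 10" per cent. For 2/40, U = 14.92% and the margin is 14.92 - 5.00 = 9.92 points, so the statement reproduces.

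**Direction.** Hold the denominator at 40. The true number of subjects with an MAE by Day 30 is the recorded m plus any unseen MAEs among the d leavers, so it is at least m. Hence m/40 is at or below the true proportion, with equality if d = 0 or no leaver had an MAE. U rises with x, so the same holds for the upper limit.

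**Size with 2 recorded MAEs.**

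| d (assumed) | Table 2 rule (leavers as non-events) | Leavers removed | Leavers as events |
|---|---|---|---|
| 0 | 2/40 = 5.00%, U 14.92% | no change | no change |
| 1 | 2/40 = 5.00%, U 14.92% | 2/39 = 5.13%, U 15.28% | 3/40 = 7.50%, U 18.26% |
| 2 | 2/40 = 5.00%, U 14.92% | 2/38 = 5.26%, U 15.66% | 4/40 = 10.00%, U 21.44% |

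Removing a leaver moves the upper limit by about 0.4 point (15.28 - 14.92 = 0.36; 15.66 - 15.28 = 0.38). Counting a leaver as an event moves it by 3.2 to 3.3 points (18.26 - 14.92 = 3.34; 21.44 - 18.26 = 3.18). The last column is a bound, not an expectation: if a leaver carries the planned 5% risk over the whole 30 days, the average addition to the rate is at most 0.05/40 = 0.125 point.

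**Does one leaver break the planning margin?** Only in one setting.

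| Events/n | Exact margin (points) | Wilson margin (points) |
|---|---|---|
| 2/40 | 9.92 | 9.03 |
| 2/39 | 10.15 | 9.24 |
| 3/40 | 10.76 | 9.85 |

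The exact method passes 10 points with one leaver; the Wilson method does not. With 1 recorded MAE the exact margin stays below 10 either way (1/39: 9.03; leaver as event, 2/40: 9.92). With 3 recorded MAEs it is already 10.76 with no leavers.

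**The case against.** The strongest reply is that Table 2 states a deliberate rule: crude incidence over essentially the whole ITT set, in a trial that is descriptive throughout (SAP 3.3). MAEs are collected as reported events, and a subject with no reported event is a non-event. Exposure is also limited. Procedural blood loss is settled before the subject leaves the operating room (Protocol L.2), and adverse events are assessed at the procedure and at discharge (Table F-2). Treatment failures and primary conversions are followed for 1 month (F.2.1.2), and loss to follow-up requires three documented contact attempts (F.7.4). The planned accountability summaries should show early exits.

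Most of this stands. It supports keeping the planned figure and explains why d is likely to be small. It does not supply the number with unknown 30-day status or show how far the rate could move.

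Three stronger readings are tempting but not supported:

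- **That Table 2 contradicts the no-imputation rule in SAP 8.3.** This is arguable at best. Counting unreported events as absent in a crude rate is an explicit definition and need not be the imputation SAP 8.3 has in mind.
- **That k, having no dates, drops subjects whose first MAE comes after Day 30 and so inflates the rate.** The cell sits under a 30-day heading opposite a dated m, so the natural meaning is no MAE in that period. This needs clearer wording and is not a demonstrated bias.
- **That treatment failures are a certain route into the problem.** The trigger counts implanted subjects, so treatment failures may not be among the 40. More generally, if early leavers are outside the 40, the misclassification does not arise for the regulatory analysis. The ITT set and the 1-day rule point to their inclusion, but the text does not settle it.

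**Conclusion.** The concern holds in a limited form. If subjects exit on Days 1-29 with no recorded MAE and are among those analysed, the 30-day crude rate and its upper limit are understated or unchanged by this rule. Neither the Protocol nor the SAP text asks for a result that bounds the effect; the separate table shells might.

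The size depends on an assumed number of exits. At 2 recorded MAEs, one leaver leaves the upper limit at 14.9% under the planned rule and takes it to 18.3% in the worst case; with no early exits there is no effect. A reader might infer that a single leaver undoes the sample-size justification. The documents do not support that. The 10-point margin is planning reasoning at 2/40 and not a limit applied to results, the SAP text does not name an exact method, and the crossing appears only at 2 MAEs with the exact interval. No pass/fail criterion exists, so the effect is on how the rate reads. Minor severity; a cheap improvement.

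**What to change.** In SAP 8.4:

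1. Keep the ITT denominator and the current figure as the main result.
2. Word k in the 30-day column as subjects with no MAE with onset on Days 0-30 (a clarification).
3. Report the number who exited the study before Day 30 without an MAE and without later documented status. Subjects still in study should not be called unknown because a compliant 1-month visit fell on Days 15-29; any later contact settles their status.
4. Show the rate and its one-sided 95% upper limit twice, with those subjects as non-events and as events.
5. State whether early leavers are among the 40.
6. Do the same for the crude 30-day rates that SAP 8.5 takes from Table 2.

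The cost is a few lines of SAP wording, one count and one extra table line per rate, using data already collected. The downside is that the second upper limit may read less favourably.

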4.2. Subset

Subset analysis will be performed by-sex for the primary endpoints descriptively and reviewed for clinical significant difference.

5. Endpoints

Primary Safety Endpoint

The primary safety endpoint is defined as the proportion of subjects experiencing a MAE within 30 days post-implantation. MAEs include the occurrence of any of the following events:

- All-cause mortality
- Bowel ischemia
- Myocardial infarction
- Paraplegia
- Procedural blood loss ≥ 1000 cc
- Renal failure
- Respiratory failure
- Stroke

Primary Effectiveness Endpoint

Technical success at the index procedure (as assessed intra-operatively) is defined as successful delivery and deployment of the Endurant Evo AAA Stent graft system in the planned location and with no unintentional coverage of both internal iliac arteries or any visceral aortic branches and with successful removal of the delivery system.

Secondary Endpoints

- All cause-mortality within 30, 183, and 365 days
- Aneurysm-related mortality within 30, 183, and 365 days
- Secondary procedures to correct Type I and III endoleaks within 30, 183 and 365 days
- Secondary endovascular procedures within 30, 183 and 365 days
- Serious adverse events within 30, 183 and 365 days
- Aneurysm rupture within 30, 183 and 365 days
- Conversion to open surgery within 30, 183 and 365 days
- Major adverse events within 183 and 365 days
- Stent graft migration at 12-month follow-up visit (as compared to 1-month imaging)
- Aneurysm expansion > 5 mm at 12-month follow-up visit (as compared to 1-month imaging)
- All endoleaks based on imaging findings at 1- month, 6-month and 12-month visits
- Stent graft occlusion based on imaging findings through 6 months and 12 months
- Device deficiencies based on imaging findings through 6 months and 12- months

Secondary endpoints will be assessed at annual follow-up visits until 5 years post-implantation.

Additional Observations

The following acute procedural observations and clinical utility measures will be reported:

- Mean duration (min) of procedure (time between initial skin access to final skin closure)
- Proportion of subjects who underwent general/local/epidural/spinal anesthesia
- Proportion of subjects who underwent unilateral/bilateral percutaneous access
- Proportion of subjects requiring blood transfusions, excluding cell saver
- Mean volume (cc) of estimated blood loss
- Mean duration (min) of radiation exposure
- Radiation exposure (mGy)

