8.5. Analysis of the Secondary Endpoints

Descriptive statistical analyses will be performed on secondary endpoints. No inferential statistical analysis is planned for secondary endpoints.

Event rates such as mortality, secondary procedures, serious adverse events, conversion to open surgery, and aneurysm ruptures will be calculated in the same way as the MAE rate, specified in Table 2.

The survival from all-cause and aneurysm-related mortality over one year time or longer will be presented with the Kaplan-Meier survival curve and the associated Kaplan-Meier estimate will be calculated along with its standard error using the Greenwood method.

Imaging based event rate such as stent graft migration, aneurysm expansion, endoleaks, stent graft occlusions, and device deficiencies will be calculated in the way as specified in Table 3.

9. Additional Data Summaries / Supplemental Analyses

Descriptive data summaries will be provided for acute procedural observations and clinical utility measures.

10. Data Screening and Acceptance

Data management will be done according to Medtronic SOPs and the Data Management Plan for this clinical study. These documents will be made available upon request.

All collected data will be reviewed for completeness, correctness and consistency. In case of issues, queries will be sent to the investigator or designee to complete, correct or comment the data.

11. List of Planned Tables, Listings, and Figures

List of planned tables, listing, and figures for the analyses can be found in a separate table shell document.

12. Appendices

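### SAP Table 2: the 30-day count of subjects without an MAE has no onset limit, so programming it as written would drop subjects whose first MAE came after Day 30

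*SAP*

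**What the plan says.** SAP section 5: "The primary safety endpoint is defined as the proportion of subjects experiencing a MAE within 30 days post-implantation". The first listed MAE component is "All-cause mortality", so a death at any time is an MAE.

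SAP section 8.4, Table 2 gives the rate as m/(m + k). In the column *Within 30 Days*:

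- m is "No. of subjects who had at least one MAE with onset day from Day 0 to Day 30, inclusive".
- k is "No. of subjects who have been in study for at least 1 day and without an MAE".

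In the next two columns, m counts onset on Days 31 to 183 and Days 184 to 365. There k requires at least 91 and 305 days in study, again with no onset limit on the MAE.

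For a subject still in the study, section 8.4 runs the duration to the lock or snapshot. It places the submission analysis at the point when 40 subjects have had the implant for at least 30 days, and says the endpoints are analysed for those 40 ITT subjects.

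Section 8.1 says an event within 30 days "is an event that takes place between Days 0 to 30, inclusive", and counts within 365 days from Day 0 to Day 365. Section 4.1 says "All analysis will be performed on the intent-to-treat (ITT) analysis set". Section 8.5 says that mortality, secondary procedures, serious adverse events, conversion and rupture rates "will be calculated in the same way as the MAE rate, specified in Table 2".

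**The concern.** The m cell writes out its window although the column header already names one. The k cell does not. Taken at its word, k asks whether a subject has had any MAE at all in the data. A subject who is well at Day 30 and dies on Day 200 is then not in m, because the onset is too late, and not in k, because the subject has had an MAE. That subject was fully observed for the 30 days that define the endpoint, yet leaves the denominator.

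The formula feeds the primary safety rate and its one-sided 95% interval. If programmed literally, a Day 0 to 30 rate could change between data cuts with nothing in Days 0 to 30 having changed, and m + k would no longer match the ITT set. Section 8.5 carries the same structure to the other event rates.

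**Working it through.** **Inputs.** Planning assumption 2 events in 40 and a stated margin below 10% (SAP 3.2); one-sided 95% binomial interval (SAP 8.4); 40 ITT subjects (SAP 8.4). Let L be the number of subjects whose first MAE came after Day 30 but before the data cut. The documents do not give L, so a range is shown.

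**Formulas.** Literal rate = m/(40 − L), if every subject meets the one-day condition. Exact (Clopper-Pearson) upper limit = 95% quantile of Beta(m + 1, n − m), with n = m + k.

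**The plan's own figure.** For 2/40 the upper limit is 14.92% and the margin is 14.92 − 5.00 = 9.92 points. This reproduces the stated margin below 10%.

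**Literal k, m = 2.**

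| L | n | Rate | Upper limit | Margin (points) | Rise in rate (points) |
|---|---|---|---|---|---|
| 0 | 40 | 5.00% | 14.92% | 9.92 | 0 |
| 1 | 39 | 5.13% | 15.28% | 10.15 | 0.13 |
| 2 | 38 | 5.26% | 15.66% | 10.39 | 0.26 |
| 4 | 36 | 5.56% | 16.47% | 10.92 | 0.56 |

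If m = 0, the rate stays at 0% and only the upper limit moves (7.22% at n = 40, 7.98% at n = 36). If L = 0, nothing changes.

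**Plausible L at submission (assumption).** Take entry uniform at 70 subjects per 12 months and a cut 30 days after the 40th entry. Entry then spans 40/70 × 365.25 = 209 days, and mean follow-up beyond Day 30 is about 104 days. With later first MAEs at 5% and 10% per year, expected L among 38 subjects is 38 × (1 − exp(−rate × 104/365.25)), or about 0.5 and 1.1.

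**Can the column header supply the missing limit?** Trace two subjects with data to Day 365. Subject A has a first MAE on Day 200 (death). Subject B has a non-fatal stroke on Day 10 and no other MAE.

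| Column | A, as written | B, as written | A, onset from Day 0 in m and k | B, onset from Day 0 in m and k |
|---|---|---|---|---|
| 30 days | neither | m | k | m |
| 183 days | neither | neither | k | m |
| 365 days | m | neither | m | m |

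Subject B shows that the header does not reliably govern the cells. Under section 8.1 a Day 10 stroke falls within 365 days, yet m in that column starts at Day 184. The 183-day column has the same pattern. Subject B also shows that limiting k alone to Day 0 onward in the later columns does not work: with m left at its late start, B remains in neither count.

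**The case against.** The strongest reply is that the cell should be read in its context. The column is headed *Within 30 Days*, section 8.1 defines that as Days 0 to 30, section 5 defines the endpoint the same way, and section 8.4 names the 40 ITT subjects. On that reading k is the complement of m, the Day 200 death stays in k, and no rate changes. The table shells, kept in a separate document (SAP 11 and 12.2), may also settle it. This stands as the likely intention for 30 days. It does not repair the text, because the later columns depart from the same definition and a programmer therefore has to follow the cells.

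Three stronger readings are tempting, and the documents do not support them.

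- A reader might infer that the primary safety rate is overstated. That needs literal programming, at least one late first MAE by the cut, and m of at least 1.
- A reader might infer that the trial misses its precision target once one subject drops out. The 10% figure is a planning precision for an assumed 2/40 in a descriptive trial, not a success criterion. It varies with the event count even at a full 40: 8.82 points with 1 event and 10.76 with 3.
- A reader might project a large inflation at 5 years. With 69 subjects and 3 early MAEs, 4.3% would become 5.0% to 6.9% if later first MAEs ran at 3% to 10% per year. Those rates are assumptions, and the plan does not schedule a repeat of the 30-day rate at 5 years. Annual reports are produced only if required (protocol H.1), and adverse event reporting narrows in years 3 to 5 (protocol F.6).

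**Conclusion.** Wrong as written, with a small effect at the submission analysis. The 30-day k cell lacks the onset limit that m has, and programming it literally contradicts the ITT denominator. The shift is 0.13 points in the rate and 0.36 points in the upper limit (15.28 − 14.92) for one dropped subject at m = 2. By this mechanism the rate can only rise or stay the same. The size rests on the assumed 2 events and on an L that the documents do not give.

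The firmer contradiction is in the 183- and 365-day columns, where m starts at Day 31 and Day 184 against the Day 0 start in section 8.1. The two need to be corrected together.

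The one-day time-in-study condition is a separate feature of the same cell. It counts early event-free leavers as non-events, which can work in the opposite direction.

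**What to change.** In Table 2:

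- *Within 30 Days*: keep m. State k as subjects in study for at least 1 day with no MAE with onset from Day 0 to Day 30, inclusive.
- *Within 183 Days*: define m as at least one MAE with onset from Day 0 to Day 183, and k as no MAE with onset in that window, keeping the 91-day condition.
- *Within 365 Days*: do the same for Day 0 to Day 365, keeping the 305-day condition.

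Every subject with an event in the window is then in m, and every other subject who meets the time-in-study condition is in k. Later events no longer alter earlier columns. In section 8.5, use the same paired definitions with the named event in place of MAE, and check that the table shells agree.

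The cost is SAP wording and an onset-date condition in the program. No additional data are needed. Changing k alone in the two later columns should be avoided, because subjects whose only MAE was early would still be in neither count.

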$n = \text{No. of Subjects Who Had Readable Images}$	No. of subjects who had a readable image within the 1-month window.	No. of subjects who had a readable image within the 6-month window.	No. of subjects who had a readable image within the 12-month window.
Event rate = m/n	Through 1 Month	Through 6 Months	Through 12 Months
$m = \text{No. of Subjects Who Had Event(s)}$	No. of subjects who had an event with scan day within the 1-month window.	No. of subjects who had an event with scan day within 1- or 6-month windows.	No. of subjects who had an event with scan day within 1-, 6- or 12-month windows.
$n = \text{No. of Subjects Who Had Readable Images}$	No. of subjects who had a readable image within the 1-month window.	No. of subjects who had an event (counted in m) or had a readable image	No. of subjects who had an event (counted in m) or had a readable image

		within the 6-month window.	within the 12-month window.
--	--	----------------------------	-----------------------------

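### The cumulative imaging rates in SAP Table 3 keep every subject with an event but drop event-free subjects who lack a last-window image, which inflates the rate when loss is unrelated to the event

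*SAP*

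**What the plan says.** SAP section 5 words two imaging endpoints cumulatively: "Stent graft occlusion based on imaging findings through 6 months and 12 months" and "Device deficiencies based on imaging findings through 6 months and 12- months". Section 8.5 assigns the method: "stent graft occlusions, and device deficiencies will be calculated in the way as specified in Table 3".

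The lower block of Table 3 (section 8.4) defines these cumulative rates as m/n. For 12 months, m is "No. of subjects who had an event with scan day within 1-, 6- or 12-month windows". The denominator n is "No. of subjects who had an event (counted in m) or had a readable image" "within the 12-month window". The 6-month column follows the same pattern. The 1-month column has one window, so the problem does not arise there.

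Three other provisions matter:
- SAP 8.3 does not impute missing images.
- SAP 8.5 plans Kaplan-Meier with Greenwood standard errors for mortality only.
- Table 3 ends at 12 months, although section 5 adds that "Secondary endpoints will be assessed at annual follow-up visits until 5 years post-implantation" and Table 1 gives analysis windows to year 5.

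**The concern.** Entry to the denominator depends on the outcome. Take two subjects who both miss the 12-month scan. One had an occlusion at 6 months and counts in m and n. The other had clean images at 1 and 6 months and counts nowhere. Death, withdrawal and missed visits therefore remove event-free subjects but cannot remove subjects whose event has already been seen.

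The stakes are highest for device deficiencies. Protocol C.5 gives stent fractures and partial detachment as the reason enrollment was stopped. A rate that rises because event-free subjects leave could be read as late device failure, and it would not be comparable with rates calculated by another method.

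**Working it through.** The plan states no expected rate, dropout rate or missing-image rate for these endpoints, so there is no figure of its own to reproduce. All loss rates below are assumptions. N = 69 is the total enrollment in Protocol C.5, and 40 is the regulatory sample in SAP 8.4.

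**1. Direction.** Let F1 be the proportion with an event before the last window, h the risk in the last window for those still event-free, and r the share of those subjects imaged in the last window. Loss is assumed unrelated to the event.
- True event-free proportion: (1−F1)(1−h).
- Table 3 event-free proportion: (1−F1)·r·(1−h) / [F1 + (1−F1)·r].
- Ratio of Table 3 to truth: r / [F1 + (1−F1)·r]. This is below 1 whenever r < 1 and F1 > 0, so the event rate is too high.

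When all events have been seen and only event-free subjects lack the last image, this reduces to m/n = F / [F + (1−F)r], where F is the true cumulative proportion. With F = 10%:

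| r | 1.00 | 0.95 | 0.90 | 0.80 | 0.70 | 0.60 |
|---|---|---|---|---|---|---|
| m/n | 10.0% | 10.5% | 11.0% | 12.2% | 13.7% | 15.6% |

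**2. Twelve months, N = 69.** Assume 4 events by 6 months, then 10 of the 65 event-free subjects without a 12-month image, then 4 events among the 55 imaged.
- Table 3: m = 4 + 4 = 8; n = 8 + 51 = 59; 8/59 = 13.6%.
- Life table: 1 − (65/69)(51/55) = 12.6%.

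**3. Early data cut, 40 subjects.** SAP 8.4 allows the regulatory analysis once 40 subjects are at least 30 days past implant, and it covers all section 5 endpoints. Assume 2 events in the 1-month window and none later. The rate through 6 months is then:
- 10 event-free subjects imaged at 6 months: 2/12 = 16.7%.
- 20 imaged: 2/22 = 9.1%.
- All 38 imaged: 2/40 = 5.0%.
- Life table in every case: 1 − 38/40 = 5.0%.

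**4. Five years, only if the same rule is carried forward.** Assume constant event and dropout hazards, independent loss, and visits at the Table 1 target days (30 to 1826). In each interval, new events are those still event-free and still followed, times the interval risk; n is cumulative m plus those event-free and still followed. Expected Table 3 rate by 5-year retention:

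| True 5-year rate | 90% | 75% | 60% | 50% |
|---|---|---|---|---|
| 5% | 5.2% | 5.6% | 6.2% | 6.7% |
| 10% | 10.4% | 11.2% | 12.2% | 13.2% |
| 20% | 20.7% | 22.1% | 24.0% | 25.6% |
| 30% | 31.0% | 32.8% | 35.2% | 37.3% |

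Relative inflation runs from about +3% (30% rate, 90% retention) to +34% (5% rate, 50% retention). The life table recovers the true rate under these assumptions. With a true 5-year rate of 10% and 60% retention, the 12-month figures are 2.15% against 2.08%, which is negligible.

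**5. Informative loss.** Assume 100 subjects and 20 true events. If 8 event subjects are lost undetected and 16 event-free subjects are lost, Table 3 gives 12/(12 + 64) = 15.8%, below the true 20%.

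**6. Two candidate repairs.** Putting everyone ever imaged in the denominator errs the other way: for a true 10% it gives 9.4% at 90% retention and 6.8% at 50%. Kaplan-Meier that censors deaths estimates risk as if nobody died. With a 5% yearly event hazard it gives 1 − exp(−0.25) = 22.1% at 5 years. If loss at 8–12% a year were all death, the proportion who actually have an event would be (0.05/0.13)(1 − exp(−0.65)) = 18.4% to (0.05/0.17)(1 − exp(−0.85)) = 16.8%.

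**The case against.** The rule is explicit and pre-specified. Requiring a last-window image has a rationale: it confirms that a subject was event-free through the time point. The analysis windows are wide and contiguous (days 305–548 for 12 months), and interim and DMC-recommended images also go to the core lab (Protocol F.3), so few subjects may be dropped. Over the written horizon, the 1-point gap in step 2 is small beside a binomial standard error of about 4.0 points, from √(0.126 × 0.874/69). The trial tests no hypothesis, secondary endpoints are descriptive, and no threshold depends on these rates.

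Most of this stands as a limit on size. It does not remove the asymmetry, since confirmation of event-free status through earlier windows is discarded when it could be used. Nor does it cover an early data cut, where event-free subjects may not yet have reached the last window.

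**Conclusion.** The point holds and should be corrected, but the size cannot be fixed from the documents. The upward direction requires loss unrelated to the event, at least one event before the last window, and at least one event-free subject without a last-window image. With complete imaging there is no effect. At 12 months it is probably small once follow-up is complete, and it may be large if the rates are reported at the minimum 30-day cut.

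A reader might infer three stronger things that the documents do not support:
- **That the plan will overstate the 5-year rates.** Table 3 stops at 12 months. The annual-assessment sentence in section 5 suggests an extension, but it would also fit the symmetric at-visit rates in the upper block of the table.
- **That the inflation must grow with time.** It grows only if the imaged share falls. With 10% of events all seen by 12 months and r falling from 0.90 to 0.60, the reported rate rises from 11.0% to 15.6% with no new event. At fixed r, the relative inflation shrinks as F rises.
- **That the comparison with other devices in Protocol J.3 rests on these rates.** J.3 refers to observations already reported, gives no figures and does not mention Table 3.

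**What to change.** For the cumulative imaging endpoints (stent graft occlusion and device deficiencies), amend SAP 8.4 and 8.5 as follows:
- Report as the main estimate a Kaplan-Meier or life-table cumulative rate by visit window with Greenwood standard error. Use scan day as event day and censor event-free subjects at their last readable image. State that scan-detected events are known only to lie between scans.
- Report alongside it the cumulative incidence with death as a competing event, because censoring deaths overstates the proportion who actually have an event.
- Write out the same rule for the annual time points to 5 years.
- Keep Table 3's m/n as a supplementary count, and show beside it the number of event-free subjects without a last-window image.

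The cost is SAP wording and one extra analysis of data already collected, using a method the SAP already plans for mortality. The drawback is that the new rates will be less directly comparable with earlier m/n tables. Neither estimator cures informative loss, so the reasons for missing last-window images should be tabulated as well.
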